5.2.2.2 Exploratory analyses

Additional relevant analyses may be identified during the conduct of the study. Any additional exploratory analyses will be outlined in the SAP prior to analysis.

5.2.3 Missing data

Full details on handling of all missing data, which are common in observational studies, will be described separately in the SAP. The proportion of missing data will be reported for each measured variable in the study. In general, missing data will not be imputed and the data will be analysed as they are recorded in the study eCRFs.

5.2.4 Limitations

As with all observational studies, one of the greatest concerns for external validity is selection bias. In order to minimise this source of bias, broad inclusion and exclusion criteria are to be applied and it is expected that most, if not all, patients indicated for treatment according to the product labeling (refer to SmPC in Appendix 2) will be eligible for enrolment in the study. In addition, sites will be instructed to invite consecutive eligible patients initially being prescribed who are planned to start or have already started treatment with single agent brentuximab vedotin as part of routine clinical care. Sites will be expected to complete a screening log which will collect a limited amount of data (e.g., age range, lymphoma type, disease stage, reason for not participating) for non-enrolled patients newly prescribed brentuximab vedotin in order to understand through descriptive analysis the representativeness of the enrolled population.

Confidential. Page 25 of 44

The risk of developing some of the AESI for this study, such as peripheral neuropathy, may be substantially affected by previous treatment regimens. The ability to assess the potential for confounding by previous exposures will be inherently limited by the completeness of the retrospective data available regarding lines of therapy. Similarly, the ability to evaluate potential risk factors for peripheral neuropathy will be limited by the availability of relevant medical history and exposure data across all patients.

Finally, the ability to meaningfully assess the safety of brentuximab vedotin in subgroups of interest, including the elderly and patients treated with more than 16 cycles of brentuximab vedotin, will be limited by the actual use of brentuximab vedotin in routine clinical care.

5.3 Data Reporting

5.3.1 Progress reports

Annual progress reports will be submitted to relevant competent authorities, as required.

5.3.2 Interim analyses and reporting

An interim analysis including both study objectives will be performed approximately 2.5 years after the first patient is enrolled.

5.3.3 Final analyses and reporting

A final study report will be generated after all data collection is complete. The final report will encompass all planned analyses, including a description of the complete study population, as described above and in the SAP. All reporting will be consistent with the STROBE (STrengthening the Reporting of OBservational studies in Epidemiology) Initiative checklist for cohort studies (STROBE 2008).

6. STUDY MANAGEMENT

This study will be performed by Quintiles (CRO), with guidance, input, review and approval of the Millennium project team, including development of materials, recruitment, training and management of sites, electronic data capture and data management and analysis. To ensure the quality and integrity of research, this study will be conducted under the Guidelines for Good Pharmacoepidemiology Practices (GPP) issued by the International Society for Pharmacoepidemiology (ISPE), the European Network of Centres for Pharmacoepidemiology and Pharmacoepidemiology, the principles outlined in the Declaration of Helsinki, and any applicable national guidelines.

6.1 Data entry/Electronic data capture

All data will be collected and entered directly into the electronic data capture (EDC) system. All sites will be fully trained on using the on-line data capture system, including electronic

Confidential. Page 26 of 44

case report form (eCRF) completion guidelines and help files. Investigators and site personnel will be able to access their account with a username and password. All eCRFs should be completed by designated, trained personnel or the study coordinator, as appropriate. In most cases, the eCRF should be reviewed, electronically signed, and dated by the investigator. All changes or corrections to eCRFs should be documented in an audit trail and an adequate explanation is required. All participating sites will have access to the data entered by the individual site on their own enrolled patients through the EDC system.

6.2 Source documents

In most cases, the source documents are contained in the patient's medical record and data collected on the eCRFs must match the data in the medical records. In some cases, the eCRF, or part of the eCRF, may also serve as source documents. In these cases, a document should be available at the investigator's site and clearly identifying those data that will be recorded in the eCRF, and for which the eCRF will stand as the source document. All original source documentation is expected to be stored at the site for the longest possible time required by local applicable regulations. The site will be instructed to notify the Sponsor before any destruction of medical records of study participants.

6.3 File retention and archiving

To enable evaluations and/or audits from regulatory authorities or the Sponsor, the investigator agrees to keep records, including the identity of all participating patients, all original signed informed consent forms, copies of all eCRFs, SAE forms, source documents and adequate documentation of relevant correspondence (e.g., letters, meeting minutes, telephone calls reports). The records should be retained by the investigator according to local regulations, or as specified in the study contract, whichever is longer.

Each site will receive a study site file at study initiation which contains all documents necessary for the conduct of the study and is updated throughout the study. This file must be available for review in the event the site is selected for monitoring, audits, or inspections and must be safely archived for at least two years after completing participation in the study. Documents to be archived include the patient enrolment log and the signed ICFs. In the event that archiving of the file is no longer possible at the site, the site will be instructed to notify the Sponsor.

6.4 Quality assurance and monitoring

A study monitoring plan, including for-cause monitoring, that is appropriate for the study design will be developed and implemented.

During the site initiation visit, the monitor will provide training on the conduct of the study to the investigator and all site staff involved in the study. In order to ensure the integrity of the

Confidential. Page 27 of 44

data, sites will be monitored. Site monitoring will be performed by clinical research associates (CRAs) to examine compliance with the protocol and adherence to the data collection procedures, to assess the accuracy and completeness of submitted clinical data, and to verify that records and documents are being properly maintained for the duration of the study. The monitor may perform source data verification by review of original patient records.

The monitor will close out each site after the last patient's final follow-up assessment is completed, all data have been entered and all outstanding monitoring issues and data queries have been resolved or addressed. All monitoring procedures and frequency of monitoring visits will be described in a Monitoring Plan. Monitor contact details for each participating site will be maintained in the Investigator Site File.

Representatives of the Sponsor's quality assurance unit/monitoring team and competent regulatory authorities must be permitted to inspect all study-related documents and other materials at the site, including the Investigator Site File, the completed eCRFs and the patients' original medical records. Audits may be conducted at any time during or after the study to ensure the validity and integrity of the study data.

6.5 Data management

A data management plan will be created before data collection begins and will describe all functions, processes, and specifications for data collection, cleaning and validation. The eCRFs will include programmable edits to obtain immediate feedback if data are missing, out of range, illogical or potentially erroneous. Concurrent manual data review will be performed based on parameters dictated by the plan. Ad hoc queries will be generated within the EDC system and followed up for resolution.

High data quality standards will be maintained and processes and procedures utilised to repeatedly ensure that the data are as clean and accurate as possible when presented for analysis. Data quality will be enhanced through a series of programmed data quality checks that automatically detect out-of-range or anomalous data.

6.6 Changes to the protocol

Changes to the protocol will be documented in written protocol amendments. Major (i.e., substantial, significant) amendments will be approved by the relevant regulatory authorities and will usually require submission or notification to the relevant IECs for approval or favorable opinion, if applicable. In such cases, the amendment will be implemented at the site only after approval or favorable opinion has been obtained.

Minor (non-substantial) protocol amendments, including administrative changes, will be filed at each participating site and will be submitted to the relevant IEC or regulatory authorities

Confidential. Page 28 of 44

where required by pertinent regulations. Any amendment that could have an impact on the patient's agreement to participate in the study requires the patient's informed consent prior to continued participation in the study.

6.7 Publication policy

Any publication of the results from this study must be consistent with the Sponsor's publication policy and guided by the Uniform Requirements for Manuscripts Submitted to Biomedical Journals: Writing and Editing for Biomedical Publication of the International Committee of Medical Journal Editors (ICMJE), updated April 2010. The rights of the Investigator and of the Sponsor with regard to publication of the results of this study are described in the Investigator contract. Any submissions for publication will be consistent with the STROBE Initiative checklist for cohort studies (STROBE 2008).

7. SAFETY REPORTING

7.1 Definitions

Adverse events (AEs)

An AE is any untoward medical occurrence in a patient or subject administered a pharmaceutical product and which does not necessarily have to have a causal relationship with the product. An AE can therefore be any unfavorable and unintended sign (including an abnormal laboratory finding, for example), symptom, or disease temporally associated with the use of a product, whether or not considered related to the product. Pre-existing conditions that worsen during a study are considered AEs.

If, according to the investigator, there is a worsening of a medical condition that was present prior to the administration of brentuximab vedotin, this should also be considered a new AE and collected in the eCRF if it meets the definitions of an SAE or AESI described below. Any medical condition present prior to the administration of brentuximab vedotin that remains unchanged or improved is not an AE.

An abnormal laboratory value should not be assessed as an AE unless that value leads to discontinuation or delay in treatment, dose modification, therapeutic intervention, or is considered by the investigator to be a clinically significant change from baseline. When possible, signs and symptoms indicating a common underlying pathology should be noted as one comprehensive event. In cases of surgical or diagnostic procedures, the condition/illness leading to such a procedure is considered as the AE rather than the procedure itself.

Serious adverse events (SAEs)

Serious AE (SAE) means any untoward medical occurrence that at any dose:

• Results in **death**.

Confidential. Page 29 of 44

- Is **life-threatening** (refers to an AE in which the patient was at risk of death at the time of the event. It does not refer to an event which hypothetically might have caused death if it were more severe).
- Requires inpatient hospitalisation or prolongation of an existing hospitalisation (planned hospital admissions or surgical procedures for an illness or disease that existed before the patient was enrolled in the study are not to be considered AEs unless the condition deteriorated in an unexpected manner during the study)
- Results in **persistent or significant disability or incapacity**. (Disability is defined as a substantial disruption of a person's ability to conduct normal life functions).
- Is a congenital anomaly/birth defect.
- Is a **medically important event**. This refers to an AE that may not result in death, be immediately life threatening, or require hospitalisation, but may be considered serious when, based on appropriate medical judgment, may jeopardize the patient, require medical or surgical intervention to prevent one of the outcomes listed above, or involves suspected transmission via a medicinal product of an infectious agent. Examples of such medical events include allergic bronchospasm requiring intensive treatment in an emergency room or at home, blood dyscrasias or convulsions that do not result in inpatient hospitalisation, or the development of drug dependency or drug abuse; any organism, virus, or infectious particle (e.g., prion protein transmitting Transmissible Spongiform Encephalopathy), pathogenic or nonpathogenic, is considered an infectious agent.

Adverse events of special interest (AESI)

For the purposes of this study, the following treatment-emergent AEs are defined as AESI, regardless of their seriousness, intensity or relationship to treatment:

- Peripheral neuropathy (sensory, motor and other)
- Neutropenia (including febrile neutropenia)
- Infections (including opportunistic infections)
- Hyperglycaemia
- Hypersensitivity reactions (including infusion-related reactions and allergic reactions)

Event intensity

Intensity for each AE, including any lab abnormality, will be determined using the NCI CTCAE (Version 4.03 effective date 14 June 2010, or higher). Clarification should be made between an SAE and an AE that is considered severe in intensity (Grade 3 or 4), because the terms serious and severe are NOT synonymous. The general term *severe* is often used to

Confidential. Page 30 of 44

describe the intensity (severity) of a specific event; the event itself, however, may be of relatively minor medical significance (such as a Grade 3 headache). This is NOT the same as *serious*, which is based on patient/event outcome or action criteria described above, and are usually associated with events that pose a threat to a patient's life or ability to function. A severe AE (Grade 3 or 4) does not necessarily need to be considered serious. For example, a white blood cell count of 1000/mm³ to less than 2000 is considered Grade 3 (severe) but may not be considered serious. Seriousness (not intensity) serves as a guide for defining regulatory reporting obligations.

Relationship to treatment

Relationship to treatment will be determined by the investigator responding yes or no to this question: Is there a reasonable possibility that the event is associated with brentuximab vedotin? This means that there are facts (evidence) or arguments to suggest a causal relationship.

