1. BACKGROUND

Relapsed and refractory CD30+ lymphomas, including the most common forms Hodgkin lymphoma (HL) and systemic anaplastic large cell lymphoma (sALCL), are rare conditions. Although both are potentially curable types of lymphoma when conventional chemotherapy regimens and radiation therapy are used, not all patients are cured with currently available front-line regimens and go on to require additional therapies.

Hodgkin Lymphoma

There is wide international variation for both males and females in HL incidence, with the highest rates in Southern Europe and Northern America. The annual age-adjusted incidence of HL in Europe in males and females is estimated at 2.1/100,000 per year [IARC 2008]. In many parts of Asia and Africa, incidence rates for Hodgkin lymphoma are 1 per 100,000 population, with the world average being around 1.2 per 100,000 for males and 0.8 per 100,000 for females [Ferlay 2010]. HL occurs in patients in all age groups and presents a bimodal distribution with peaks at 15 to 35 years of age and over the age of 60 [Cartwright 2004]. Classical HL is defined histopathologically by the presence of malignant Hodgkin and Reed-Sternberg cells in a background of inflammatory cells. First line treatment for HL is typically ABVD [Adriamycin® (doxorubicin), bleomycin, vinblastine, dacarbazine] or BEACOPP (bleomycin, etoposide, Adriamycin, cyclophosphamide, Oncovin®, proparbazine, prednisone), but other older options (e.g., MOPP – mechlorethamine, Oncovin, procarbazine, prednisone) and alternating regimens may be used [Furtado 2012]. Approximately 10 to 20% of patients presenting with HL will become refractory to initial therapy or relapse. Salvage therapy after relapse varies widely. Autologous hematopoietic stem-cell transplantation (ASCT) is a viable option for only some patients with recurrent or progressive HL after failure of initial combination chemotherapy, and it is only effective in half of such patients [Sureda 2005, Majhail 2005]. Patients who subsequently relapse after stem cell transplant have an extremely poor prognosis [Moscowitz 2004, Horning 2008].

Systemic Anaplastic Large Cell Lymphoma

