4.2.1 Inclusion Criteria

To be eligible for enrolment, patients must meet all of the following criteria:

- Age at enrolment ≥ 18 years
- Clinical diagnosis (with histologic confirmation) of relapsed or refractory CD30+ HL or relapsed or refractory sALCL
- Patient is planned to start or is already receiving single agent therapy with brentuximab vedotin as part of routine clinical care

Confidential. Page 16 of 44

• Willing and able to provide informed consent

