4.4.2 Effectiveness measures

The focus of this study is safety; therefore no measures or analyses regarding treatment effectiveness are included in the study.

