5.2.2 Planned analyses

5.2.2.1 Primary analyses

Serious Adverse Events (SAEs) and Adverse Events of Special Interest (AESI)

SAEs and AESI (including both serious and non-serious AESI) will be summarized by MedDRA system organ class (SOC) and preferred term (PT). Frequency and incidence proportion for all SAEs and AESI (as defined in Section 4.4.1) will be reported for patients who received at least one dose of brentuximab vedotin while on study.

The incidence rate and the associated 95% CI will be reported for SAEs and AESI.

Time at risk of SAEs and AESI will correspond to current/recent treatment with brentuximab vedotin. Current/recent treatment will be defined as time between the dates of first and last dose plus 30 days. All other follow-up time accrued for the patient will be considered occurring during past treatment with brentuximab vedotin; events reported during the past treatment period will be presented separately.

In addition, select events will be displayed by timing in relation to treatment start (e.g., by number of completed cycles) or time-to-event analysis may be carried out using Kaplan-Meier plots for the occurrence of the first reported occurrence of the adverse event, as appropriate for the event.

Identification and Description of Risk Factors for Peripheral Neuropathy

In addition, multivariable adjusted analysis will be performed to identify and describe risk factors for peripheral neuropathy (e.g., BMI, previous history of neuropathy, known toxic exposures) in the cohort. Risk factors for the first occurrence of new onset or worsening of peripheral neuropathy will be explored using a multivariable adjusted Cox regression model. Model assumptions concerning proportionality will be evaluated graphically in the usual manner. The inclusion of specific risk factors will be described in the SAP. A preliminary univariate analysis of the association of variables of interest with the outcome measure will be

Confidential. Page 24 of 44

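### Section 7.1 does not exempt progression of the treated lymphoma from the AE rule, so the overall SAE proportion and rate in 5.2.2.1 partly reflect disease progression

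*Protocol*

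**What the plan says.** **AE rule.** Protocol section 7.1 says that "Pre-existing conditions that worsen during a study are considered AEs". It repeats the rule for a "worsening of a medical condition that was present prior to the administration of brentuximab vedotin, this should also be considered a new AE", to be collected if it meets the SAE or AESI definition.

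**Who has such a condition.** Section 4.2.1 requires of every patient a "Clinical diagnosis (with histologic confirmation) of relapsed or refractory CD30+ HL or relapsed or refractory sALCL".

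**Seriousness.** "Serious AE (SAE) means any untoward medical occurrence that at any dose" meets one of the listed criteria, among them death, a threat to life, and inpatient or prolonged hospitalisation. Causality is not a condition. The one nearby exception is for planned admissions or procedures for a disease that predates enrolment, which "are not to be considered AEs unless the condition deteriorated in an unexpected manner during the study".

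**Recording window.** Section 7.2 has all SAEs recorded from first dose through 30 days after last dose. From day 31, only SAEs judged related to the drug are recorded.

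**Analysis.** Section 5.2.2.1 states: "Frequency and incidence proportion for all SAEs and AESI (as defined in Section 4.4.1) will be reported", and adds the incidence rate with its 95% CI. Time at risk runs from first to last dose plus 30 days. Sections 4.4.1, 5.2.1 and 5.2.2.1 also plan tables by system organ class and preferred term, an evaluation of relationship to treatment, summaries by age group and by enrolment cohort, and, where appropriate, by lymphoma type and by more than 16 cycles.

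**Effectiveness.** Section 4.4.2 says that the focus is safety and "therefore no measures or analyses regarding treatment effectiveness are included in the study".

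**The concern.** The general AE rule reaches the one disease that every patient has, and the protocol does not say how its progression is to be handled. Progression is foreseeable here: section 1 says of Hodgkin lymphoma that "Patients who subsequently relapse after stem cell transplant have an extremely poor prognosis".

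The overall SAE proportion and rate would then combine two things: untoward events during treatment, and failure of the disease to respond. The figures most exposed are the comparative summaries. A group with more aggressive disease would show a higher SAE incidence even if all its other SAEs were equally frequent. Two further effects are inferences, not statements in the protocol:

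- If patients who progress tend to stop treatment, progression SAEs would fall mainly among those with 16 or fewer cycles.
- Patients enrolled while already on treatment had survived to consent, so fatal progression before enrolment cannot appear in the retrospective cohort.

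Because section 7.1 does not mention the treated lymphoma, sites may also differ in whether they apply the rule to it.

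**Working it through.** **1. Does progression meet the definition?** Set the sections side by side:

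- The lymphoma predates the drug in every patient (4.2.1).
- Its worsening is an AE (7.1, stated twice).
- If it leads to death, a threat to life, or an unplanned or prolonged admission, it is serious (7.1). The planned-admission exception covers neither death nor an unplanned admission.
- Between first dose and last dose plus 30 days it is recorded whatever its cause (7.2), and that window is the time at risk (5.2.2.1).
- No section exempts it.

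So it counts in the all-SAE proportion and rate.

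**2. The plan's own figures.** Table 2 in section 5.1 is the only precision calculation. A normal approximation with continuity correction, p ± (1.96·√(p(1−p)/500) + 1/1000), reproduces every non-zero row. For 10 events: 0.02 ± (0.0123 + 0.001) gives 0.7% to 3.3%. The zero row matches the exact upper limit, 1 − 0.025^(1/500) = 0.74%. No stated figure is wrong. Table 2 concerns individual AESI, so this point does not depend on it.

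**3. Size on assumed rates.** The protocol gives neither an SAE rate nor a progression rate. Let b be the share of patients with another SAE in the window (assumed 20-40%) and a the share with a progression SAE (assumed 5-20%), taken as independent. Then:

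any-SAE proportion = b + (1 − b)·a, so the increase is (1 − b)·a.

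| b | a = 5% | a = 10% | a = 20% |
|---|---|---|---|
| 20% | 24.0% (+4.0) | 28.0% (+8.0) | 36.0% (+16.0) |
| 30% | 33.5% (+3.5) | 37.0% (+7.0) | 44.0% (+14.0) |
| 40% | 43.0% (+3.0) | 46.0% (+6.0) | 52.0% (+12.0) |

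The increase is 3 to 16 points, or 7.5% (3/40) to 80% (16/20) in relative terms. With N = 500 the 95% half-width of these totals is 3.7 to 4.4 points, and the increase exceeds it in seven of the nine cells.

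Independence matters. With no overlap between the two kinds of patient the increase is a itself, up to 20 points. If every patient with a progression SAE also has another SAE, it is zero.

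**4. Effect on a comparison.** Take two subgroups, each with b = 30%, one with a = 5% and one with a = 20%. Their any-SAE proportions are 33.5% and 44.0%, a gap of 10.5 points with no difference in other SAEs.

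**5. Can the planned tables undo this?** Take b = 30% and a = 10% in 500 patients: 150 with another SAE, 50 with a progression SAE and 15 with both, so 150 + 50 − 15 = 185 (37.0%) with any SAE. A reader who sees 185 overall and 50 under progression terms knows only that the count without progression lies between 135 (27%) and 185 (37%). The actual 150 (30%) needs patient-level data.

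**The case against.** **All-cause SAE collection is a legitimate design.** Objective 1 is to evaluate the occurrence of SAEs, not of drug-attributable ones. This stands. A reader might infer that counting progression contradicts section 4.4.2. It does not: an untoward event counted as an SAE is not an effectiveness measure or analysis.

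**The scope is limited.** A reader might infer that every admission or death from progression counts. Planned admissions are exempt unless the deterioration was unexpected, and unrelated events from day 31 after the last dose are not recorded. The five AESI categories are untouched, and the sample size rests on them.

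**Other planned tables help.** Preferred-term tables make progression visible, and the relationship evaluation sets apart events judged related. Section 5.2.1 also compares disease history and performance status between cohorts. All this helps, but none of it gives the patient-level SAE incidence without progression. Relatedness is a yes/no investigator judgement that answers a different question.

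**It belongs in the SAP.** A term list and an extra table row can sit there, and the SAP is not at hand. If it already has them, only the recording line remains. That line is a protocol matter: section 7.1 fixes the general rule, and an SAP cannot make sites record progression alike.

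**No testing is planned, and worse disease also raises other SAEs.** Both are true. Removing progression terms would not make subgroups comparable; it would remove one identifiable component of the difference.

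**Conclusion.** The point holds as a consequence of a stated rule. Section 7.1 brings serious progression of the treated lymphoma within the SAE definition, and section 5.2.2.1 counts it in the overall SAE proportion and rate and their subgroup and cohort summaries, for events from first dose through 30 days after last dose. Those figures therefore partly reflect disease progression.

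The size cannot be derived from the protocol. The 3 to 16 percentage points rest wholly on assumed rates of 20-40% and 5-20% and on independence. If patients who progress also tend to have other SAEs, the increase is smaller.

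A reader might go further and conclude that the safety results are invalid or that the drug will look less safe than it is. The documents do not support that: the all-cause figure is a proper quantity, the AESI results stand, and no printed number is wrong. This is a cheap improvement in how the overall SAE figures can be read.

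**What to change.** - **Unchanged:** SAE collection and reporting to pharmacovigilance.
- **Section 7.1:** add one line on how sites record progression of the treated lymphoma and death from it, using a uniform verbatim description that is then coded centrally in MedDRA.
- **Section 5.2.2.1:** report the overall SAE proportion and rate, including by subgroup and cohort, in two forms: all SAEs, and all SAEs except a list of lymphoma-progression preferred terms fixed before the data cut.

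**Cost:** one protocol line, one term list and one extra row per overall SAE table, with no new visits or data items. Enrolment began in June 2013, so descriptions recorded before the change would need a central check. The downside is a second SAE figure to explain. It will still contain progression-driven events recorded as symptoms or organ failure, and the report should say so.
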